6.1.3 Demographic and Baseline Characteristics

Patient demographics will be summarized and listed for patients in the ITT population. Reports will include age as a continuous variable as a categorical variable (≤ 50 , >50 to 65 , >65), gender, ethnicity, race, smoking status, baseline height (cm), baseline weight (kg), and BMI (kg/m^2). Data will be presented by treatment arm as well as overall for the study.

COVID-19 disease history will be summarized and listed. These will include: number of comorbidities, the number and percentage of patients with 1, 2, or 3+ comorbidities, number of symptoms at time of hospitalization and a breakdown by symptom (n and %), days since self-reported first symptom, days since self-reported fever, days since date of positive test. Derivation of 'days since' variables will use date of randomization as the reference date.

6.1.4 Medical History

Medical history will be collected during screening and will be summarized by MedDRA coded system organ class (SOC) and preferred term (PT) by treatment arm and overall. All patient data will also be listed.

The following co-morbidities will be identified based on medical history and will be summarized in addition to the overall medical history. Medical co-morbidities include:

- Hypertension
- Diabetes
- Cardiovascular disease
- Congestive heart failure or myocardial infarction

6.1.5 Prior and Concomitant Medication

Prior medication collection was limited to medications required for review of entry criteria. Current medications and new medications prescribed while on study were collected in the eCRF. Medications will be summarized by anatomical therapeutic chemical (ATC) level 2 classification and preferred name as coded by WHODD. A subject will be counted only once at each level of reporting.

Prior medications are those which have been identified to have been discontinued prior to the treatment start date. Concomitant medications are those with a start date prior to date of first dose of study treatment and ongoing at time o

f treatment or which have been prescribed and taken after first dose of study treatment. Prior medications will be listed only. Concomitant medication will be summarized and presented by treatment group.

All prior and concomitant medication data will be listed including the verbatim and preferred drug name and ATC Level 2.

6.1.6 Study Drug Exposure and Compliance

Patients randomized to study treatment are to receive their first dose on Day 1 and a second dose on Day 8. All effort will be made for patients who remain in the hospital on Day 8 to receive their second dose of study treatment. If the patient is discharged prior to Day 8, no second dose will be administered.

Compliance will not be assessed in this study as sites are administering study treatment. As the disease in nature may progress quickly, the expectation is that at least 1 dose of study treatment will be given.

The number and percentage of patients who receive 1 dose and 2 doses will be summarized by treatment arm and overall. The planned dose level and total dose administered will be descriptively summarized by dose received.

Study treatment administration details, including reasons for not administering drug and if there were issues with the administration will be listed.

6.2 Efficacy

Analyses and summary statistics will be reported on the mITT population. Efficacy endpoints are assessed up to Day 28. All data will be listed. Sensitivity and supplemental analyses may be repeated in other analysis populations.

6.2.1 Primary Efficacy Endpoint and Analyses

The primary objective of the study is to evaluate the effect INB03 + SofC has on disease progression compared with placebo + SofC. Disease progression is defined as death or requirement for mechanical ventilation in participants with pulmonary complications from COVID-19 infection. The primary endpoint to assess the objective is to compare the proportion of patients who reach disease progression in both treatment arms. Disease progression will be assessed up to Day 28. Patients will be identified as follows:

1 = Disease progression – defined as developing the need for mechanical ventilation or death by Day 28. Mechanical ventilation includes CPAP, BIPAP, or mechanical ventilation requiring intubation.

0 = No disease progression – defined as not developing the need for mechanical ventilation or death by Day 28

The null hypothesis is that there is no difference in the proportion of patients who have disease progression between treatment groups and the alternative is that the proportion of INB03 treated patients with disease progression is less than the proportion of placebo patients with disease progression.

$$H_0: P_{INB03} = P_{Placebo} \text{ vs } H_1: P_{INB03} < P_{Placebo}$$

Statistical analysis of the primary endpoint will be performed with a one-sided level of significance and final alpha of $\alpha=0.005$.

6.2.1.1 Primary Estimand

Treatment Arms	INB03 (1mg/kg) + SofC and Placebo + SofC, given via subcutaneous injection.
Target Population	Randomized participants who have been diagnosed with COVID-19, have at least one co-morbidity, are admitted to the hospital and have pulmonary complications due to COVID-19 who receive any amount of study drug.
Endpoint	Proportion of participants with disease progression from randomization to 28 days post-randomization. Disease progression is defined by the development of need for mechanical ventilation or death. Mechanical ventilation includes CPAP, BIPAP or mechanical ventilation requiring intubation.

Population Summary	Difference between treatment arms in proportion of disease progression by day 28	
Analysis Method	Stratified Cochran-Mantel-Haenszel	
Intercurrent events	Event	Strategy
	Withdraw consent prior to Day 28	While on treatment – data prior to event is of interest
	Lost to Follow-up prior to Day 28 with no hospital discharge date	Composite variable – event is considered informative about patient's outcome
	Lost to Follow-up prior to Day 28 with a hospital discharge date	Treatment policy – data is used as if event never occurred
	Did not receive Dose 2 on Day 8	Treatment policy – data is used as if event never occurred
	Discontinued from study for reasons other than Withdrawal of consent or Lost to Follow-up prior to Day 28	Treatment policy – data is used as if event never occurred
	Receipt of prohibited medication prior to Day 28	Treatment policy – data is used as if event never occurred
	Did not receive mechanical ventilation due to unavailability	Hypothetical – data is used assuming event did not occur

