5.4 Handling of Withdrawal or Termination

Participants withdrawing from the study will be encouraged to complete the same final evaluations as participants completing the study according to this protocol (Day 40 assessments).

Reasonable efforts will be made to contact participants who are lost to follow-up. Investigator will be expected to try as much as possible to re-connect those participants at the end of the trial in order to obtain at least their vital status. These efforts must be documented in the participant's file.

Investigators will be trained about the importance of participant retention and steps to prevent missing data.

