9.5.1 Primary Endpoint

The primary estimand will be estimated based on the mITT population and includes randomized participants who have been diagnosed with COVID-19, have at least one co-morbidity, are admitted to the hospital and have pulmonary complications due to COVID-19 who receive any amount of study drug. To estimate this estimand, all post-randomization data up until Day 28 of the study will be used in the evaluation of treatment difference regarding disease progression. The estimator is the proportion of participants with disease progression up until Day 28 post-randomization where disease progression defined as is administration of mechanical ventilation or death.

As specific intercurrent events may occur that could lead to missing or spurious data, the following strategies will be used.

- Participant withdraws consent and has missing disease progression data: The “Treatment Policy” strategy for this event will be employed. The last available post-randomization record of the WHO Ordinal Scale for Clinical Improvement will be used to identify disease progression. If mechanical ventilation or death data are missing from the database, and if the last available post-randomization score is 7 or greater, the participant will be considered to have disease progression for the primary analysis of the primary endpoint.
- Participant is lost to follow-up and have no hospital discharge date and data regarding disease progression is missing: The “Composite” strategy for this event will be used. Participants with this intercurrent event are considered to have disease progression. This strategy assumes participants who remain in the hospital but are lost to follow-up for any reason are assumed to have disease progression. Similarly, participants who are discharged from the hospital and do not have information collected up to Day 28 are assumed to have disease progression.
- Participant is lost to follow-up and has a hospital discharge date and data regarding disease progression is missing: The “Treatment Policy” strategy for this event will be employed. The last available post-randomization record of the WHO Ordinal Scale for Clinical Improvement will be used to identify disease progression. If mechanical ventilation or death data are missing from the database, and if the last available post-randomization score is 7 or greater, the participant will be considered to have disease progression for the primary analysis of the primary endpoint.

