9.5.1.2 Sensitivity Analysis

Alternative methods for handling of intercurrent events will include the following:

- Participants who withdraw consent and have missing disease progression data: The “Composite” strategy will be used. Participants will be considered as having disease progression.
- Participants who withdraw consent and have missing disease progression data: Participants randomized to Placebo will use the “While on Treatment” strategy for this event as described for the primary estimand and participants randomized to INB03 will use the “Composite” strategy.

A tipping point analysis allowing the handling of missing data in the two study arms to vary independently to determine thresholds where there is no longer evidence of a difference in the primary endpoint will be conducted.

Additional sensitivity analyses may be defined in the SAP.

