- Summary statistics will not exceed four digits after the decimal. Some laboratory parameters or other data may require judicious deviation from this rule.

Unless otherwise noted, statistical inference will be based on a 2-sided 1% significance level.

All data up to the time of study completion/withdrawal from the study will be included in the analysis, regardless of duration of treatment.

Numbering for data displays will be based on ICH E3.

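### The protocol and SAP disagree on how consent withdrawal is handled in the primary estimand, and the SAP does not say whether ventilation or death known to have occurred after withdrawal, but by Day 28, is counted

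*SAP*

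**What the plan says.** Protocol 9.5.1 sets the data scope of the primary estimand: "all post-randomization data up until Day 28 of the study will be used in the evaluation of treatment difference regarding disease progression". For withdrawal it states: "Participant withdraws consent and has missing disease progression data: The “Treatment Policy” strategy for this event will be employed". Where the outcome is missing, the last WHO ordinal record decides, with progression assigned "if the last available post-randomization score is 7 or greater".

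Protocol 9.5.1.2, in a sensitivity analysis for the same event, describes the primary strategy differently: "Participants randomized to Placebo will use the “While on Treatment” strategy for this event as described for the primary estimand".

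SAP 6.2.1.1 and 6.2.1.3 list withdrawal of consent before Day 28 as while on treatment, with the gloss "data prior to event is of interest". If the outcome is missing, the last WHO record before withdrawal is used. SAP Appendix 2 defines while on treatment as concerned with response before the intercurrent event. SAP 5.1 adds a general rule: "All data up to the time of study completion/withdrawal from the study will be included in the analysis, regardless of duration of treatment".

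Two other SAP statements point the other way. SAP 6.2.1 codes a participant as progressed for ventilation or death by Day 28, with no exception for withdrawal. The opening of SAP 6.2.1.3 limits imputation to cases where ventilation or death information is missing.

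On collection, Protocol 5.4 says: "Participants withdrawing from the study will be encouraged to complete the same final evaluations as participants completing the study". Note 12 to the Schedule of Assessments has disease progression assessed from randomization to Day 40.

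**The concern.** Take a participant who withdraws on Day 5 while on oxygen, agrees to the final evaluations, and is then found to have been ventilated on Day 9. Under Protocol 9.5.1 this is progression. Under the SAP estimand row and the SAP 5.1 cut, read literally, the Day 9 event lies outside the data of interest and the participant scores 0. Under SAP 6.2.1 and the opening of 6.2.1.3, the same participant scores 1. Two programmers could code this participant differently and each cite the SAP.

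The endpoint includes death, and withdrawal by hospitalised patients may be related to outcome. Setting aside known events would undercount failures in whichever arm had more withdrawals, or sicker ones. The hypothesis is one-sided in favour of INB03, so an undercount in that arm favours the drug. SAP 1.1 also removes both sensitivity analyses aimed at withdrawal and relies on the tipping point analysis, which varies the handling of missing data. That could treat a known event as a hypothetical one, but would not simply count it. SAP 6.2.2.1 extends the 6.2.1.3 rules to days to progression: early terminators classed as not progressed are given the longest duration, 40 days.

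**Working it through.** **Step 1: the passages applied to a known Day 9 ventilation after a Day 5 withdrawal.**

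| Place | Rule | Result |
|---|---|---|
| Protocol 9.5.1 | Treatment policy, all data to Day 28 | Counts |
| Protocol 9.5.1.2 | Attributes while on treatment to the primary estimand | Set aside, if literal |
| SAP 6.2.1 | Progression means an event by Day 28 | Counts |
| SAP 6.2.1.1, 6.2.1.3 (row), Appendix 2 | While on treatment | Set aside, if literal |
| SAP 6.2.1.3 (opening) | Impute only if the outcome is missing | Not missing, so counts |
| SAP 5.1 | Data included up to withdrawal | Set aside by implication |

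The protocol and the SAP each give both answers.

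**Step 2: where the label matters.** In SAP 6.2.1.3 the missing-data method for withdrawal is the same as for two treatment-policy rows: loss to follow-up with a discharge date, and discontinuation for other reasons. Protocol 9.5.1 also carries the last WHO record. When the outcome is missing, the rules therefore nearly coincide, except that the protocol gives a cut-off of 7 and the SAP row gives none. The label can change a result only when ventilation or death is observed after withdrawal.

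**Step 3: the planned sample size, as a reference.** Inputs (Protocol synopsis and 9.1): 21% vs 7%, one-sided alpha 0.005, 90% power, 1:1 allocation. With the unpooled two-proportion formula, n = (2.576 + 1.282)² × [0.21 × 0.79 + 0.07 × 0.93] / 0.14² = 14.88 × 0.2310 / 0.0196 = 175.4, so 176 per arm against the stated 173. Power at 173 per arm is 89.5% (unpooled) or 88.5% (pooled). Allowing for 5% untreated, 173 / 0.95 = 182.1, so 183 per arm and 366 in total, as stated. The planned N does not depend on the withdrawal rule, so there is no corrected N.

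**Step 4: size per event.** SAP 6.2.4 reports 77 dosed. Assuming an even split, 77 / 2 is about 38 per arm, and one event is 1/38 = 2.6 percentage points.

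**Step 5: illustrative ranges.** The documents give no withdrawal rate. Assume that a share w = 2% to 10% withdraw and that q = 7% to 50% of those progress afterwards by Day 28. Assume also that every such event is known and then set aside; events never observed are handled almost identically under either label.

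- Events set aside, w × q × n: among 77, from 0.02 × 0.07 × 77 = 0.1 to 0.10 × 0.50 × 77 = 3.9 in total, or at most about 1.9 per arm. At 173 per arm, 0.2 to 8.7 per arm.
- Power at 173 per arm (pooled), equal withdrawal of 2/5/10% with all events among those withdrawn set aside: 88.5% falls to 87.6/86.2/83.5%.
- Type I error at 173 per arm, true rate 21% in both arms, withdrawal in the INB03 arm only, so that its counted rate is 0.21 − w × q: with w = 2/5/10%, 0.0066/0.0098/0.018 at q = 21%, and 0.0095/0.023/0.084 at q = 50%, against a nominal 0.005.
- At the planned result (36 vs 12 events of 173), counting 7 further INB03 events would move one-sided p from 0.0001 to 0.0062.

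**The case against.** The strongest reply is that nothing in the SAP says a known event after withdrawal is coded 0. SAP 6.2.1 has no exception for withdrawal, and a known Day 9 ventilation is not missing, so carry-forward is never triggered. This stands: a score of 0 is the literal result of the estimand row and the data cut, not an explicit rule. SAP 5.1 is also a general default saying what is included, not a rule written for the primary endpoint.

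A reader might infer that the SAP quietly replaced a clear protocol strategy. The documents do not support that. Protocol 9.5.1.2 already attributes while on treatment to the primary estimand, and SAP 1.1 repeats that sentence when deleting the sensitivity analysis. The SAP authors may have seen no change to list.

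A reader might also infer that sites must collect outcomes after withdrawal. Protocol 5.4 only encourages the final evaluations and does not say whether they take place at withdrawal or later. Its vital-status search is for loss to follow-up. Protocol 12.3 says that those who withdraw written consent should not continue. Observed post-withdrawal events may therefore be few.

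Finally, if post-withdrawal data are cut, the outcome is arguably missing and so falls within the tipping point analysis. That is a fair reading, but it still treats a known outcome as unknown.

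**Conclusion.** The conflict is real. Protocol 9.5.1 disagrees with Protocol 9.5.1.2 and with SAP 6.2.1.1 and 6.2.1.3, and within the SAP the estimand row and the 5.1 cut disagree with 6.2.1 and the opening of 6.2.1.3. SAP 1.1 does not list the departure from Protocol 9.5.1. The consequence is limited to ventilation or death observed after withdrawal and by Day 28, in participants with no qualifying earlier record. Such data exist only for those who agree to the Protocol 5.4 evaluations or whose outcome is otherwise lawfully available.

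The total size is unknown. The only firm measure is about 2.6 points per event, assuming about 38 dosed per arm. A reader might multiply this up: three events in one arm would be 3/38 = 7.9 points against a planned difference of 14. No withdrawal count in the documents supports that. The power and error figures rest on assumed rates and on full knowledge of post-withdrawal events, so they illustrate direction and range only. The change is still worth making, because it removes an ambiguity in the primary endpoint at little cost.

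**What to change.** In SAP 6.2.1.1 and 6.2.1.3, set withdrawal of consent before Day 28 to treatment policy, as in Protocol 9.5.1. State that any death or mechanical ventilation known to have occurred by Day 28 counts, whether before or after withdrawal, where the participant agreed to the evaluations or the fact is otherwise lawfully available. Carry the WHO score forward only when the outcome is truly missing, and state the cut-off in the SAP row. Exempt the primary endpoint from the SAP 5.1 cut at withdrawal, so that its limit is Day 28. Correct the label in Protocol 9.5.1.2. If the sponsor prefers while on treatment, SAP 1.1 should list it as a change with a reason, and SAP 6.2.1 should be made to agree. The choice should be settled before the unblinded preliminary analysis described in SAP 6.2.4.

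The cost is wording only, with no new data collection. The downside is that post-withdrawal data will be incomplete and available only for those who agree, so some outcomes will still be imputed.

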6.2.1.2 Primary Analysis

The primary endpoint is binary in nature and will be analyzed using a stratified Cochran-Mantel-Haenszel (CMH) test. Stratification factors of Age (≤ 50 , >50 to 65, >65) and number of comorbidities (1, 2, 3+) will be included to compare the response rate of INB03 + SOC to Placebo + SOC. Treatment differences, odds ratios (ratio of odds in INB03 + SOC arm to the odds in Placebo + SOC only arm) and the 95% confidence interval will be provided. If expected cells counts are not sufficient for each strata, strata levels will be combined for the analysis as follows:

- Age will be split by the median in the mITT population (ie: $<$ median, \geq median)
- 1-2 comorbidities vs. 3+ comorbidities

If still not sufficient, a non-stratified Chi-square analysis will be conducted instead of CMH.

The number and percentage of patients with disease progression by Day 28 will be summarized by treatment arm.

6.2.1.3 Handling Missing Data

The following intercurrent events may lead to missing data for the primary endpoint. Imputation will be performed when the primary endpoint of mechanical ventilation or death information prior to Day 28 is missing.

Intercurrent Event	Strategy	Method of handling missing data
Withdraw consent prior to Day 28	While on treatment – data prior to event is of interest	the last available post-randomization record of the WHO Ordinal Scale for Clinical Improvement, prior to the intercurrent event, will be used to assess disease progression
Lost to Follow-up prior to Day 28 with no hospital discharge date	Composite variable – event is considered informative about patient's outcome	the participant will be considered to have disease progression
Lost to Follow-up prior to Day 28 with a hospital discharge date	Treatment policy – data is used as if event never occurred	the last available post-randomization record of the WHO Ordinal Scale for Clinical Improvement, prior to the intercurrent event, will be used to assess disease progression
Discontinued from study for reasons other than Withdrawal of consent or Lost to Follow-up prior to Day 28	Treatment policy – data is used as if event never occurred	the last available post-randomization record of the WHO Ordinal Scale for Clinical Improvement, prior to the intercurrent event, will be used to assess disease progression
Did not receive mechanical ventilation due to unavailability	Hypothetical – data is used assuming event did not occur	the last available post-randomization record of the WHO Ordinal Scale for Clinical Improvement, prior to the intercurrent event, will be used to assess disease progression

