6.1.2 Protocol Deviations

Protocol deviations will be identified and classified as minor or major (violations) before the database is locked. Major protocol deviations include and are not limited to:

- Violation of Inclusion/Exclusion Criteria
- Signed incorrect version of patient consent form
- Use of prohibited therapies
- Receiving incorrect randomized treatment
- Did not receive mechanical ventilation due to the machine not being available

Each protocol deviation will be reviewed prior to database lock and the deviations that are identified as having an impact on the primary study endpoint will be flagged and patients with those deviations will be excluded from the PP population.

Protocol deviations will be summarized by treatment arm and overall for the study.

A listing of protocol deviations will be provided.

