7.2 APPENDIX 2: Estimand Terminology

Source: ICH E9 R1

Strategy	Description
Treatment policy	The occurrence of the intercurrent event is irrelevant: the value for the variable of interest is used regardless of whether or not the intercurrent event occurs.
Composite Variable	The occurrence of the intercurrent event is taken to be a component of the variable, i.e. the intercurrent event is integrated with one or more other measures of clinical outcome as the variable of interest.
Hypothetical	A scenario is envisaged in which the intercurrent event would not occur: the value to reflect that scientific question of interest is that which the variable would have taken in the hypothetical scenario defined.
Principal stratum	The target population might be taken to be the principal stratum (see Glossary) in which an intercurrent event would not occur.
While on treatment	Response to treatment prior to the occurrence of the intercurrent event is of interest.

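### When no ventilator is available, SAP 6.2.1.3 scores a surviving participant's first unmet need for ventilation as no progression, which conflicts with the endpoint and with the row's own strategy

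*SAP*

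**What the plan says.** SAP 6.2.1 codes a participant as 1 for disease progression, "defined as developing the need for mechanical ventilation or death by Day 28". The estimand table in SAP 6.2.1.1 agrees: "Disease progression is defined by the development of need for mechanical ventilation or death". Both count CPAP and BIPAP as mechanical ventilation, as does Protocol 4.2.1. Protocol 9.5.1, however, describes the estimator with "disease progression defined as is administration of mechanical ventilation or death".

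SAP 6.2.1.1 and 6.2.1.3 add an intercurrent event that the protocol does not list: "Did not receive mechanical ventilation due to unavailability". Its strategy is hypothetical, glossed as "data is used assuming event did not occur". The method cell in 6.2.1.3 then takes the last post-randomization record of the "WHO Ordinal Scale for Clinical Improvement, prior to the intercurrent event, will be used to assess disease progression". A sentence above that table limits imputation to cases where ventilation or death information before Day 28 is missing.

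SAP 6.1.2 names the same event among the major deviations: "Did not receive mechanical ventilation due to the machine not being available". Deviations judged on review to affect the primary endpoint remove a participant from the per-protocol (PP) population.

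**The concern.** Someone who goes without a ventilator only because none is available has developed the need for one. Under the endpoint as defined, that outcome is known and equals 1. The row treats it as an outcome to be inferred, and infers it from a time before the need arose. A carried-forward score cannot show a need that had not yet occurred.

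The primary endpoint value is at stake. Two programmers working from the same documents could score the same participant differently, and one of those scores would contradict the endpoint. With 77 dosed participants, single events carry weight.

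**Working it through.** This is mainly a check of one rule against the definitions around it. Arithmetic enters only for scale.

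**1. Possible WHO scores before the event.** On the scale in Protocol 16.1, levels 7 to 9 all require mechanical ventilation in progress and level 10 is death. Level 6 is non-invasive ventilation or high-flow oxygen; level 5 is oxygen by mask or nasal prongs. Exclusion criterion 2 (Protocol 5.2) keeps out patients in immediate need of intubation, CPAP or BIPAP, so a first need arises after entry. Before a first unmet need, a living participant therefore scores at most 6.

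**2. Cut-off.** The SAP gives no score that counts as progression. The only one in the documents is 7 or greater, in Protocol 9.5.1, where it is set for withdrawal, loss to follow-up after discharge, and other missing data.

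**3. Strategy.** SAP Appendix 2 (7.2) defines the hypothetical strategy: "A scenario is envisaged in which the intercurrent event would not occur". The event here is unavailability. Without it the participant would have been ventilated, so the value is 1.

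**4. Scores side by side.**

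| Participant | Endpoint as defined | WHO row with cut-off 7 | Hypothetical strategy |
|---|---|---|---|
| First need unmet, alive at Day 28 | 1 | 0 (score at most 6) | 1 |
| First need unmet, dies by Day 28 | 1 | not needed; death recorded, 1 | 1 |
| Already on CPAP or BIPAP, then no invasive ventilator | 1 | not needed; ventilation recorded, 1 | 1 |
| Already intubated earlier | 1 | not needed; ventilation recorded, 1 | 1 |

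Only the first line conflicts. Lowering the cut-off to 6 would not mend it: a participant on mask or nasal oxygen scores 5, and level 6 mixes high-flow oxygen with non-invasive ventilation.

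**5. Scale.** Inputs: 77 dosed (SAP 6.2.4), 1:1 allocation, and planned rates of 21% and 7% (SAP 3.3).

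- Planning check: the unpooled formula gives (2.576 + 1.282)² × (0.21 × 0.79 + 0.07 × 0.93) / 0.14² = 175.4, so 176 per arm or 352 in total, within 2% of the stated 346. The scoring point does not depend on this figure.
- Average arm size: 77 / 2 = 38.5. One case moves an arm's rate by 1 / 38.5 = 2.6 percentage points.
- Expected events at the planned rates: 38.5 × 0.21 + 38.5 × 0.07 = 8.1 + 2.7 = 10.8. One case is about 9% of them.
- Illustration with assumed counts (unstratified pooled Z): 3/38 on INB03 against 8/39 on placebo gives Z = −1.58. Rescoring one placebo event to 0 gives −1.31; rescoring one INB03 event instead gives −1.99. None of these reaches the one-sided 0.005 level (−2.576).
- Assumed equal loss in both arms at the planned 173 per arm: pooled power is 88.5% with no loss, 86.2% if 5% of events are rescored, and 83.5% if 10% are.

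**The case against.** The best defence is the missing-data condition. SAP 6.2.1.3 imputes only when ventilation or death information is missing; a documented need is not missing, so SAP 6.2.1 scores it 1 and the row never operates. That is a fair reading and gives the right value. But it leaves the row without a purpose, although the SAP lists this event expressly as one to be resolved from the WHO record. The protocol's reference to administration supports the opposite reading, in which an unventilated participant has no endpoint information. The condition makes the score ambiguous; it does not settle it.

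Several limits stand in full:

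- A reader might infer that every participant without a ventilator who survives is scored 0. The documents do not support that: anyone already on CPAP or BIPAP (WHO level 6) or intubated had progressed, and the value 0 depends on a cut-off borrowed from the protocol.
- A reader might infer that known failures have been counted as successes. No case of unavailability is reported, and the number may be zero.
- A reader might infer bias towards INB03. Nothing links unavailability to arm in this blinded trial. Loss unrelated to arm would mainly shrink the difference, while with few events the result could move either way.
- PP exclusion is not automatic. It follows only if review finds an effect on the primary endpoint, and PP is a secondary population.

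The tipping point analysis (SAP 6.2.1.4) varies missing-data handling by arm, but reaches these participants only if they are flagged as missing. It does not correct the primary score.

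**Conclusion.** The concern holds for one group: participants whose first need for CPAP, BIPAP or intubation was unmet for lack of a device and who are alive at Day 28. For them the WHO row, read with the protocol's cut-off, gives 0, while the endpoint definition and the row's stated strategy give 1. The missing-data condition offers a way out, but the texts disagree on whether it applies, so the primary endpoint has no single defined value for these participants.

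The size cannot be stated beyond the effect per case: about 2.6 percentage points in one arm at 77 dosed, and about 9% of expected events if the planned rates held. The Z values and power figures above rest on assumed counts and show scale only. The documents do not support a claim that the trial's result is biased, or in which direction. The defect lies in the rule for the primary endpoint and should be corrected whatever the count.

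**What to change.** - In SAP 6.2.1.1 and 6.2.1.3, state that a documented need for mechanical ventilation by Day 28, unmet because no device was available, counts as disease progression (1). The hypothetical label can stay if applied as Appendix 2 defines it; a composite label gives the same value.
- Delete the WHO carry-forward for that row.
- In Protocol 9.5.1, replace administration with need, to match Protocol 4.2.1.
- In SAP 6.1.2, state that this event alone does not exclude a participant from the PP population.

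The cost is a SAP amendment, which SAP section 1 permits before final database lock and unblinding, plus the protocol wording. It should be settled by staff blind to allocation. It also needs a check that the unmet need and its date are recorded in the eCRF or the deviation log; the documents do not show that they are, so some retrieval from source records may be required.
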